4.1.5. Sample Size

Power calculations for this trial were carried out within the logistical and practical constraints of the trial; in particular, a maximum of 25 sites are available for randomization, whereas the intervention can be implemented at only 10 sites. Consistent with previous clinical trials, we would consider a minimum relative reduction of 50% in the repetition rate to be both clinically important and achievable [47-49]. To conduct an accurate power calculation, we obtained data from ICES regarding the number of presentations with selfharm by men and the re-presentation rate to every hospital in Ontario from 2012 to 2014. Using these data, we calculated an anticipated baseline repetition rate (primary outcome) after 12 months of 13%. We also calculated an intracluster correlation coefficient (ICC) of 0.01 and an inter-period correlation of 0.008 (to account for over time correlations between pre- and post-intervention measures of the primary outcome). Given an average cluster size of 80 men and a coefficient of variation of cluster sizes (to account for imbalances in sizes) of 30%, 10 intervention clusters and 15 control clusters (2000 men) achieve 90% power to detect the minimum important difference. With 80% power, the detectable difference is a relative reduction of 41%, i.e., from a control arm rate of 13% to an intervention arm rate of 7.7% (an absolute reduction of 5.3%).

> Study Protocol Version 1, Date: December 1, 2017 Page 20 of 51

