Health condition(s) or problem(s) studied	Self-harm
Intervention(s)	Intervention: smartphone-assisted Problem-Solving Therapy (PST)

World Health Organization Trial Registration Data Set Items

DATA CATEGORY	INFORMATION
	Control: standard clinical care
Key inclusion and exclusion criteria	Ages eligible for study: ≥18 years Sexes eligible for study: Male Accepts healthy volunteers: No Inclusion criteria: adult patient (≥ 18 years); patient identifies as male, patient presents to Emergency Department for an index episode of intentional self-harm at an eligible Emergency Departments in Ontario, Canada. Exclusion criteria: patient presents to an eligible Emergency Department for a reason other than intentional self-harm.
Study type	Interventional Allocation: randomized, unbalanced Intervention model: parallel assignment Masking: none Primary purpose: prevention
Date of first enrolment	Pending
Target sample size	25 hospitals; anticipated total sample size of approximately 2,000 men
Recruitment status	Active, not yet recruiting
Primary outcome(s)	Composite measure of suicides and/or proportion of re-presentations to any Emergency Department in Ontario for intentional self-harm
Key secondary outcomes	Within one year of enrollment:
	• Number of suicides;
	• Proportion of self-harm re-presentations to any

DATA CATEGORY	INFORMATION
	Emergency Department in Ontario;
	• Proportion of re-presentations for any reason to any Emergency Department in Ontario;
	• Proportion of hospital admissions for any reason to any hospital in Ontario;
	• Length of stay at any hospital in Ontario for any reason;
	• Proportion of hospital outpatient appointments for any reason at any hospital in Ontario;
	• Number of deaths (mortality rate), for reasons other than suicide and undetermined deaths;
	• Proportion of primary care visits, defined as any visit to a general practitioner;
	• Total health care costs for the treatment of self-harm;
	• Physician costs for the treatment of self-harm;
	• Emergency Department costs for the treatment of self-harm;
	• Hospitalization costs for the treatment of self-harm;
	• Other costs related to the treatment of self-harm.

Table of Contents

1.	FUNDI	NG	8
2.	ROLES	AND RESPONSIBILITIES	8
2	.1. Contr	ibutorship	8
	2.1.1.	Author's Contributions	9
	2.1.2.	Sponsor contact information	9
2	.2. Com	nittees	9
	2.2.1.	Principal Investigator and co-Principal Investigator:	9
	2.2.2.	Steering Committee (refer to title page for membership)	9

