3.4. Trial Design

This is a pragmatic, multicentre pre- and post-design cluster RCT comparing the offer of a service that delivers smartphone-assisted PST to usual care, in men who present to the Emergency Department with self-harm. We have chosen a cluster randomized design because we are testing the introduction of a service for suicidal men that addresses both the need to manage the transition from the Emergency Department to outpatient care and the provision of care specifically designed for men who have intentionally self-harmed.

By randomizing entire sites with a waiver of informed consent for data collection with inclusion of all eligible men using routinely collected data, external validity of the study is maximized, in comparison to an individually randomized trial with a requirement to seek informed consent (refer to Section 5.3 Consent).

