4.3.3. Statistical Methods

Outcomes

The unit of analysis will be the individual patient. To evaluate the effectiveness of the complex intervention at population-level (primary trial analysis), all outcomes will be obtained from ICES, regardless of whether men received or participated in the study therapy. Dichotomous primary and secondary outcomes will be described, by arm, using frequencies and percentages. The primary composite outcome as well as its individual components (completed suicides and re-presentations within 1 year) will be compared between the intervention and control sites using generalized linear mixed effects regression, accounting for the pre-and post-intervention measures using repeated cross-sectional analysis [51]. Differences between the arms will be expressed as absolute and relative differences in proportions, together with 95% confidence intervals. Models will account for clustering at the Emergency Department level and over time using random effects. Cluster level covariates for factors used in the allocation procedure, namely urban/rural, onsite psychiatric service, and size will be included in regression models. Additional analyses will adjust for individual prognostic variables including age, ethnicity, pre-specified comorbidities (such as previous hospitalizations for substance use), and repeat as compared with first-time presentations for self-harm.

All binary secondary outcomes (representation to the ED for any reason, admission to hospital for any reason, and mortality for any reason) will be analyzed as described for the primary outcome. Length of hospital stay for any reason, number of hospital outpatient appointments, number of primary care appointments and cost data will be analyzed as described for the primary outcome, that is, using generalized linear mixed effects regression, but with either the Poisson or negative binomial distribution and using the log link function. Differences between the arms will be expressed as rate ratios together with 95% confidence intervals.

Additional subgroup analyses will be carried out for the following subgroups: first time presentations of self-harm compared to repeat presentations; Francophone versus Anglophone; men with substance abuse disorders versus no substance abuse disorder; and rural versus urban residence.

Health Economic Evaluation

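### Does the sample size of 2,000 men count only one period of a pre/post design, and do the two stated powers then disagree?

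*Protocol*

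**What the plan says.** Section 4.1.5 takes 10 intervention and 15 control sites and sets out the cluster sizes thus: "Given an average cluster size of 80 men and a coefficient of variation of cluster sizes" of 30%. Its other inputs are a 12-month repetition rate of 13%, an ICC of 0.01 and an inter-period correlation of 0.008. It then gives two results. The first is that "10 intervention clusters and 15 control clusters (2000 men) achieve 90% power to detect the minimum important difference", that difference being a 50% relative reduction (13% to 6.5%). The second is 80% power for a 41% reduction, to 7.7%.

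The registration table at the front of the protocol gives the target as "25 hospitals; anticipated total sample size of approximately 2,000 men".

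Section 3.4 describes the trial in these words: "This is a pragmatic, multicentre pre- and post-design cluster RCT comparing the offer of a service". Section 4.3.3 compares the arms with a mixed model that uses the pre- and post-intervention data as repeated cross-sections, with random effects for site and time, and reports 95% confidence intervals.

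**The concern.** Two things look wrong.

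**The count.** If both periods are analysed and 80 is the number of men per site in one of them, the analysed set is larger than 2,000, yet the registration table calls 2,000 the total. If instead 2,000 covers both periods, each site supplies only about 40 men per period. That would be half the post-intervention information, and the trial would miss both stated powers.

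**The two powers.** Both come from one design and so share essentially one standard error. On usual two-sided formulas, 80% power at 7.7% implies about 93–95% at 6.5%, while 90% at 6.5% implies only about 72–75% at 7.7%. Read as exact figures, 90% and 80% do not go together. If the 90% were the exact one, the 41% claim would be too optimistic.

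**Working it through.** **Inputs from the protocol.** 10 and 15 sites; mean size m = 80; CV 0.30; ICC 0.01; inter-period correlation 0.008; control rate 13%; intervention rate 6.5% or 7.7% (all section 4.1.5). **Assumed:** two-sided 5%, in line with the 95% intervals of section 4.3.3, and equal pre- and post-periods wherever the pre-period is used.

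**Count.** 25 × 80 = 2,000 exactly, so each site is counted once.

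**Design effect.** DE = 1 + ((1 + CV²)m − 1) × ICC.
- m = 80: 1 + (1.09 × 80 − 1) × 0.01 = 1.862. Effective sizes: 800/1.862 = 429.6 and 1,200/1.862 = 644.5.
- m = 40: 1 + (1.09 × 40 − 1) × 0.01 = 1.426. Effective sizes: 400/1.426 = 280.5 and 600/1.426 = 420.8.

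**Reproducing the plan's figures.** For a post-period comparison, power = Φ[(d − 1.96·SE_pooled)/SE_unpooled].
- m = 80, 7.7%: d = 0.053, pooled rate (10 × 0.077 + 15 × 0.13)/25 = 0.1088, SE_pooled 0.01939, SE_unpooled 0.01846. (0.053 − 0.0380)/0.01846 = 0.81, power **79.2%**. The reduction detectable with 80% power is 41.2%, against the stated 41%.
- m = 80, 6.5%: d = 0.065, SE_pooled 0.01901, SE_unpooled 0.01780. (0.065 − 0.0373)/0.01780 = 1.56, power **94.0%**.
- m = 40, 6.5%: SE_pooled 0.02353, SE_unpooled 0.02203. (0.065 − 0.0461)/0.02203 = 0.86, power **80.4%**.
- m = 40, 7.7%: SE_pooled 0.02400, SE_unpooled 0.02285. (0.053 − 0.0470)/0.02285 = 0.26, power **60.3%**.

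**Using the pre-period.** The correlation of a site's two period means is r = 1.09 × 80 × 0.008/1.862 = 0.375, reading 0.008 as a between-period ICC. Baseline adjustment multiplies the variance by 1 − r² = 0.860. A pure change contrast multiplies it by 2(1 − r) = 1.251.

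| m = 80 per site-period, two-sided 5% | Power at 6.5% | Power at 7.7% |
|---|---|---|
| Post-only, mixed pooled/unpooled z (above) | 94.0% | 79.2% |
| Post-only, unpooled, t with 23 df | 93.8% | 78.5% |
| Post-only, arcsine z | 94.6% | 80.4% |
| Baseline-adjusted, pooled, t with 23 df | 94.0% | 80.6% |
| Baseline-adjusted, mixed pooled/unpooled z | 96.7% | 85.0% |
| Change contrast, unpooled z | 90.4% | 72.8% |
| Change contrast, pooled, t with 23 df | 83.3% | 64.4% |

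Several ordinary formulas come within about two points of 80% at 7.7%, and all of those shown also exceed 90% at 6.5%.

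**The split reading.** With 40 men per site-period, the highest two-sided power over all the variants run (post-only, baseline-adjusted and change contrasts; six variance or effect-scale forms; z and t; with and without the CV term) is 86.9% at 6.5% and 67.8% at 7.7%. It delivers neither statement.

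**Plausibility.** Section 4.1.2 requires sites to average at least 50 male self-harm presentations a year, so 80 is credible as roughly one year's intake at a site.

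**The case for a change.** The strongest case for a change is that the protocol publishes power figures whose validity depends on things it leaves out. It gives no period for the 80, no pre-intervention count, no alpha and no contrast. A reader who takes the registration table literally and spreads 2,000 men over both periods gets neither power. The contrast matters too: with 80 per site-period a pure change contrast stays well below 80% at 7.7% (72.8% and 64.4% in the two versions shown).

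Part of this stands. The label is missing, and that 2,000 is a post-intervention count is an inference from the power figures, not something the text says.

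The rest does not carry far. The split into 40 and 40 appears nowhere in the document. Section 4.1.5 ties the 2,000 to intervention and control sites, and the arms differ only after the service starts. The registration table gives a target next to the date of first enrolment; the pre-period consists of records from before the service began, and leaving them out of a target is a defensible convention. On the two powers, a design with 94% power achieves 90%, so nothing false is stated. A few one-sided 5% variants even bring both figures within two points, again only with 80 per site-period.

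Nor do the figures identify the contrast. Post-only and baseline-adjusted formulas both fit the 80%, while one change contrast (90.4%) fits the 90%. Writing in exact powers from one chosen model would add precision that the document does not support. Section 4.3.3 already names the model class, the random effects and a cited method; the exact contrast is ordinary material for a statistical analysis plan, which is not shown.

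**Conclusion.** The concern does not call for a change. On the natural reading, 80 men per site in the post-intervention period, the stated 80% at a 41% reduction is reproduced to within about two points by several standard formulas. The stated 90% at a 50% reduction is then a floor, with about 93–95% available. No shortage of men or sites is shown, and the looseness in the 90% figure runs in the conservative direction.

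What remains is unwritten detail that alters no result if the plan is followed as it stands.

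This rests on a two-sided 5% test. The post-only results do not depend on the inter-period correlation; the baseline-adjusted results also assume equal periods and 0.008 as a between-period ICC. If 0.008 were instead the correlation of site means, baseline adjustment would gain almost nothing, and the pooled t version would give about 90.5% and 74.3%. That would still meet the 90% claim but fall short of 80% at 41%. A pure change contrast would also fall short there, but the protocol does not commit to one.

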4.1.6. Study Timeline

4.2. Assignment of Interventions

4.2.1. Allocation to Intervention

To minimize the risk of imbalances between the study arms, allocation to the intervention or control arm was implemented using covariate constrained allocation [50]. Allocation was constrained based on: i) geographic areas, defined by whether the catchment area was predominantly urban or rural; ii) whether there was an onsite psychiatric service which assesses people in the Emergency Department; iii) size defined by the average number of presentations for self-harm for both men and women over a 3 year period; and iv) representation rate among men with intentional self-harm 12 months after the index episode. There was a total of over 3 million possible allocations of 10 intervention and 15 control sites, of which 7,131 of 100,000 randomly selected allocations met the pre-specified balancing constraints, namely a maximum difference of 3 between number of urban/rural

Study Protocol Version 1, Date: December 1, 2017 Page 21 of 51 sites, a maximum difference of 3 in number of sites with onsite psychiatric service, a maximum difference in mean cluster size of 60, and a maximum difference in baseline representation rate of 3%. Among the 7,131 possible acceptable allocations, one allocation was selected at random using a computer-generated random number.

4.2.2. Blinding

Once randomization was complete, study sites allocated to the intervention arm were approached regarding their interest to participate in the study. Gatekeepers were not approached prior to randomization as the investigative team determined that informing 25 sites and getting their agreement prior to randomization would result in significant delays to the study and that it was unlikely that hospitals would decline to participate in this study. Additionally, there were concerns regarding changes in institutional behaviour at the control sites as a result of knowing about the study. Should any intervention sites refuse to participate in the trial, they will be included in the final analyses as part of the intervention arm in order to respect the intent-to-treat (ITT) principle.

Control sites will be unaware of their participation in the study as men who present with self-harm will be receiving their usual care and all outcome measures are routinely collected by ICES.

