4. METHODS

4.1. Participants, Interventions and Outcomes

4.1.1. Study Setting

This multicenter cluster RCT will be conducted in 25 Emergency Departments in Ontario. The unit of randomization is selected Emergency Departments in each region (refer to Appendix A for a complete list of intervention and control sites).

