5. ETHICS AND DISSEMINATION

5.1. Research Ethics Approval

Trial design and conduct has been informed by TCPS 2 and ICH GCP, an international ethical and scientific quality standard for designing, conducting, recording and reporting trials that involve the participation of human subjects. Compliance with these standards provides public assurance that the rights, safety and well-being of trial subjects are protected, consistent with the principles that have their origin in the Declaration of Helsinki, and that clinical trial data are credible. This study protocol will be reviewed and approved by the Research Ethics Board (REB) of Record, as assigned by Clinical Trials Ontario (CTO), and any other local REB required by participating sites. Subsequent to initial review, the Principal Investigator will complete progress reports, to be submitted to the REB annually, which will describe the progress of the trial, including recruitment and follow-up rates, participant safety and any changes to the study protocol and/or Informed Consent Forms.

This study protocol will be published in *Trials Journal*, will be reported in accordance with CONSORT guidelines for cluster randomized trials [55], and will be registered with clinicaltrials.gov.

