5.3. Consent

5.3.1. Waiver of Consent

In order to appropriately address the research questions and objectives of this study, we will be requesting a waiver of informed consent from the 25 Emergency Departments to be included in this study. We will not ask patients presented to Emergency Departments for their consent to take part in the study as the outcome data that we are collecting are already routinely collected by ICES. As per the Tri-Council Policy Statement: Ethical Conduct for Research Involving Humans (TCPS 2), an exception to the requirement to seek prior consent may be requested if the clinical trial meets the following criteria:

- 1. The research involves no more than minimal risk to the participants;
- 2. The alteration to consent requirements is unlikely to adversely affect the welfare of participants;
- 3. It is impossible or impracticable to carry out the research and to address the research question properly, given the research design, if the prior consent of participants is required;
- 4. In the case of a proposed alteration, the precise nature and extent of any proposed alteration is defined; and
- 5. The plan to provide a debriefing (if any) which may also offer participants the possibility of refusing consent and/or withdrawing data and/or human biological materials, shall be in accordance with Article 3.7B [56].

We will be conducting a sub-study of the effectiveness of smartphone-assisted PST at the intervention sites. Eligible patients in this sub-study will be consented and enrolled according to TCPS 2 and GCP recommended guidelines. There are numerous precedents of studies analyzing ICES data which do not ask for individual patient consent to use their data [57].

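### Control EDs are to be kept unaware of the trial, but the protocol lists them in an appendix, circulates and publishes that protocol without a stated embargo, and leaves unclear whether they are contacted about the waiver.

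*Protocol*

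**What the plan says.** Section 4.2.2 (Blinding) makes an unqualified statement: "Control sites will be unaware of their participation in the study". The same sentence gives as grounds that men there receive usual care and that outcomes are collected routinely. The section explains that hospitals were not approached before randomization because of delay and because refusal was thought unlikely. It then gives a further reason: "there were concerns regarding changes in institutional behaviour at the control sites as a result of knowing about the study".

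Four other places bear on whether control sites can stay unaware:

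- Section 4.1.1 (Study Setting): "refer to Appendix A for a complete list of intervention and control sites".
- Section 4.4.3 (Study Monitoring): the study protocol is the first item covered at each site initiation meeting, which all study team members for that site attend.
- Section 5.1 (Research Ethics Approval): "This study protocol will be published in" a named journal, and the trial "will be registered with clinicaltrials.gov".
- Section 5.3.1 (Waiver of Consent): the investigators will be "requesting a waiver of informed consent from the 25 Emergency Departments".

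Section 4.1.5 gives the split of the 25 departments as 10 intervention and 15 control.

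**The concern.** The protocol identifies a specific bias, namely control hospitals altering what they do because they know about the trial, and answers it with a statement that they will not know. It sets out no procedure to keep that true. The document that names the control sites is also the one to be reviewed with intervention-site staff and published.

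The comparison is with usual care at the 15 control departments over the year after the index episode. If those departments learn of their role during that time, two things could change:

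- assessment, referral or follow-up of men who self-harm, which would alter the true repetition rate;
- recording of self-harm in the routine data, which would alter the measured rate without any change in the men's outcomes.

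Either would mean that the control arm no longer represents undisturbed usual care.

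**Working it through.** No figure in the plan is at issue, so the check is a comparison of sections.

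**1. Does the protocol identify the control sites?** Section 4.1.1 says Appendix A covers both intervention and control sites. The table of contents titles it as a complete list of study sites. The table itself was not in the copy read, so this step rests on the protocol's own description of it. Whether arms are marked in a column or by separate lists is not known.

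**2. Who sees the protocol before follow-up ends?** Under section 4.4.3, every intervention site reviews it at initiation, before recruitment begins. Under section 2.2.2, the co-investigators at each intervention site sit on the Steering Committee, which approves the final protocol. Staff at up to 10 hospitals could therefore see which other Ontario departments are controls. No section asks them to keep this confidential or says that Appendix A is removed from their copy.

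**3. Does publication add to this?** Section 5.1 plans journal publication. It gives no date, does not say whether Appendix A is included, and does not tie publication to the end of follow-up. No readable content under section 4.1.6 (Study Timeline) settles the date.

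**4. Does the waiver request reach control sites?** The count is 10 + 15 = 25, so the 25 departments named in section 5.3.1 include all 15 controls. The sentence admits three readings:

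| Reading | Control EDs contacted? | Consistent with 4.2.2? |
|---|---|---|
| Request addressed to the 25 departments | Yes, all 15 | No |
| Waiver covering patients seen at the 25 departments | No | Yes |
| Waiver of the departments' own agreement | No | Yes |

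Section 5.1 places review with the REB of Record and with any local board that participating sites require. It does not say whether a control site counts as participating, so it does not resolve the ambiguity.

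**5. Which way would the bias run?** Improved care at control sites lowers their true event rate and dilutes the effect. Improved coding can do the opposite: section 3.1.1 describes chronic under-detection of self-harm in Ontario, so better recording could raise the control count and enlarge the apparent benefit.

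**6. Would the trial see it?** Sections 3.4 and 4.3.3 describe a pre- and post-intervention comparison using repeated cross-sections. A shift in control rates against baseline could be visible. The data could not separate a shift caused by awareness from a secular trend.

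**The case against.** The strongest reply is that no contradiction is proven. Publication is undated and would do no harm after follow-up, and the journal article need not carry Appendix A. The rest of section 5.3.1 concerns patients' consent to use of routine data, so its waiver sentence most naturally refers to patients. Section 4.2.2 bases unawareness on usual care and routine data, not on secrecy, and gives behaviour change only as an additional reason. Under section 4.1.3 the control sites receive no training, materials or referral option, and seeing a hospital's name in an appendix supplies none of these.

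Much of this stands. A reader might infer that the statement on unawareness and the other sections cannot both be followed. The documents do not support that, because delayed publication, a withheld appendix and a waiver directed to the ethics board would reconcile them. A reader might also infer that registration discloses the control sites, but the registration data shown at the front of the protocol give only the number of hospitals and a generic description.

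What the reply does not remove is that none of the reconciling steps is written down. Site initiation review also precedes follow-up, whatever the publication date.

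**Conclusion.** The point holds as a gap between an asserted safeguard and the steps the protocol prescribes. Followed as written, the plan can disclose control-site status during follow-up, and the waiver sentence leaves open whether the 15 control departments are contacted directly. This rests on section 4.1.1's description of Appendix A being accurate and on the circulated copies containing that appendix.

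The size and direction of any bias cannot be derived from the document. A reader might be tempted to assume that awareness lowers the control event rate by some fraction and to convert that into lost power. The protocol gives no basis for such a fraction, and section 3.2 reports no clear relationship between the nature or intensity of standard hospital care and repetition. Nor can it be said that the effect necessarily shrinks, since improved coding could work the other way. The case for acting is that the protocol itself names the risk and that preventing it is cheap.

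**What to change.** Two changes:

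1. **Appendix A.** Withhold the control-site names, or the arm assignment, from every version that is published or sent to sites until outcome follow-up ends, then disclose the full list. State this in section 4.2.2, with cross-references in 4.1.1, 4.4.3 and 5.1.
2. **Section 5.3.1.** Reword it to say that the waiver is sought from the REB of Record, and from the data custodian if required, for use of data on men seen at the 25 departments, and that control departments are not contacted.

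Neither change touches the design, sample size, care or analysis. The cost is some transparency during the trial, because readers of the published protocol would see the control list only after follow-up. A dated commitment to disclose it limits that cost.
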